## **INTRODUCTION**

Lupus nephritis (LN) may affect approximately half of patients with Systemic Lupus Erythematosus (SLE). LN is a major cause of morbidity and the most important predictor of mortality in patients with SLE (1,2). Some 5-20% of patients with LN may develop end-stage renal disease within 10 years of follow-up from the time of diagnosis (3). Other studies have described progression to end-stage renal disease in 10-30% of patients with LN (4,5).

The European League Against Rheumatism (EULAR), the European Renal Association (ERA) and the European Dialysis and Transplant Association (EDTA) have recently updated their recommendations for the management of LN. These recommend the use of intravenous (IV) methylprednisolone boluses followed by lower doses of oral glucocorticoids (GC) and place mycophenolate mofetil (MMF) and the European regimen of cyclophosphamide (CYC) as the immunosuppressive drugs of first choice, with the IV CYC regimen for certain more aggressive cases. They also consider the use of "multitarget therapy" based on the combination of tacrolimus (TAC) and MMF and GC in patients with proteinuria in the nephrotic range who have not responded to the first line of treatment. For refractory active renal disease, they recommend as an alternative the use of rituximab (RTX) 1000 mg IV repeated after 15 days (6).

Recently, belimumab has been shown to be significantly more effective than placebo in the treatment of patients with active LN (7). This finding will lead to positioning belimumab in the therapeutic algorithm for LN.

However, in clinical practice these immunosuppressive drugs are not always effective in the treatment of LN, and even one in 3 patients with an initial favorable response may experience renal recurrence (3).

The choice of the appropriate treatment for LN and its early initiation are key to improve the prognosis of these patients and to avoid progression to chronic renal failure.

The identification of biomarkers capable of predicting the response (or lack thereof) to one or another therapy at the time of LN diagnosis would allow to implement precision medicine, thus constituting a revolution in the treatment of patients with LN. Being able to make personalized therapeutic decisions, based on the biological characteristics of each patient's renal sample, allows more targeted treatments with greater specificity to be established.

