#### Sample size

For this proof-of-concept study, our objective is to analyze around **60 renal biopsy** samples (expandable according to the results obtained).

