**Variables will be collected to establish different patterns of response to treatment and evolution of LN:**

- a) complete renal response, defined according to EULAR/ERA-EDTA recommendations (13): proteinuria  $<0.5$  g/24 hours and (near) normal estimated GFR.
- b) partial renal response, defined according to EULAR/ERA-EDTA recommendations (13):  $\geq 50\%$  proteinuria reduction to subnephrotic levels and (near) normal eGFR
- c) no response: all the other cases.
- d) proteinuria levels at 12 months of treatment,
- e) renal relapse as defined as reproducible increase in uPCR to  $>1$  g if the baseline value was  $<0.2$  g, to  $>2$  g if the baseline value was between  $0.2$  g and  $1$  g, or more than twice the value at baseline if the baseline value was  $>1$  g AND/OR reproducible decrease in GFR of  $>20\%$ , accompanied by proteinuria ( $>1$  g), and/or RBC and/or WBC cellular casts (yes/no and number of flares), e) time to first flare, f) chronic renal failure,
- f) end-stage renal disease requiring dialysis and/or renal transplantation.

Data collection will be based on the clinical history of the patients included in the study.

Confidentiality will be respected in accordance with RD 1720/2007 and the Data Protection Laws. Approval will be requested from the **Galician Clinical Research Ethics Committee (CEIC)** as well as from the CEIC of each center, if necessary.

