## **STATISTICAL ANALYSIS**

In the descriptive study, numerical variables will be expressed as mean  $\pm$  standard deviation (SD) or median and interquartile range (IQR), depending on whether the distribution is normal or not, respectively. We will establish 2 groups of patients, according to the response to treatment and the clinical evolution of the patient with LN (i.e., complete remission yes/no). To establish differences between patients in these 2 groups, we will use the  $\chi^2$  test for categorical variables or Fisher's exact test when the expected frequencies are small, the t-Student test for normal continuous variables, and the Mann-Whitney U test for variables with non-normal distribution.

Different methods to analyze and/or mitigate the missing data problem will be used.

The percentage of positive cells and staining intensity will be correlated with the different patterns of response to treatment and evolution of LN.

Univariate and multivariate linear logistic regression analyses will be performed to explore the relationships between the different variables studied (clinical, histopathological, therapeutic...) and the presence of the different renal outcomes (dependent variable). Values of  $p < 0.05$  will be considered significant.

We will carry out other different statistical methods according to the results that we observe from our initial analysis.

Statistical analyses will be performed by the Statistical Specialist of the IRIDIS Group.

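### Logistic regression is planned for rare renal outcomes such as end-stage renal disease without a sparse-data method or a named test; with roughly 3-18 events, categorical predictors and multivariable models can separate

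*Combined protocol and SAP*

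**What the plan says.** - **Model.** Statistical Analysis: "Univariate and multivariate linear logistic regression analyses will be performed", relating clinical, histopathological and treatment variables to "the presence of the different renal outcomes (dependent variable". A p-value below 0.05 is the only decision rule. The section does not say whether the p-value comes from a Wald, likelihood-ratio or score test. It names no penalised or exact logistic method, no minimum number of events and no limit on covariates.
- **Outcome.** The list of response and evolution variables ends with "end-stage renal disease requiring dialysis and/or renal transplantation".
- **Size.** Sample size: "For this proof-of-concept study, our objective is to analyze around" "60 renal biopsy" samples, expandable, with no power calculation or event forecast.
- **Event rates.** The Introduction gives two: "Some 5-20% of patients with LN may develop end-stage renal disease within 10 years of follow-up", and "Other studies have described progression to end-stage renal disease in 10-30% of patients with LN". The second has no time horizon.
- **Small-sample provision.** The section allows "Fisher's exact test when the expected frequencies are small". This belongs to the two-group comparisons, and the only grouping given there is whether complete remission was reached.
- **Fallback.** A general sentence allows further methods, to be chosen in the light of the first results.

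**The concern.** When every event falls in one level of a predictor, or some combination of covariates splits events from non-events, the logistic likelihood has no finite maximum. Software then prints a huge coefficient with a huge standard error, or drops the variable. The Wald p-value, which is the usual default in logistic output, goes to about 1.

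This is not ordinary over-fitting. It can happen with one categorical predictor, and it hides true associations instead of inflating noise. The study's purpose is to find biopsy features that predict renal outcome, and end-stage disease is the gravest of the renal outcomes listed. A strong categorical predictor of it could be reported as non-significant with no usable odds ratio. With the test left open, the same table can also be read as p=0.999 or p=0.003, and the choice would be made after the data are seen.

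**Working it through.** The target of about 60 has no stated derivation, so there is no plan figure to reproduce.

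**1. Expected events** (N × rate, one biopsy per patient)
- First range: 60 × 0.05 = 3 to 60 × 0.20 = 12.
- Second range: 60 × 0.10 = 6 to 60 × 0.30 = 18.
- Together: about 3-18. Binomial 95% ranges are 0-7 at 5%, 2-11 at 10%, 6-18 at 20% and 11-25 at 30%.

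**2. One separated table.** Assume 6 of 30 marker-positive and 0 of 30 marker-negative patients have the event.
- Maximum likelihood: log odds ratio about 22, SE about 14,500, Wald p=0.999.
- Likelihood ratio: 2[6 ln(6/30) + 24 ln(24/30) − 6 ln(6/60) − 54 ln(54/60)] = 2(−15.01 + 19.50) = 8.99 on 1 df, p=0.0027.
- Fisher: p=0.024.
- Firth (in a 2×2 table, add 0.5 to each cell): OR = (6.5 × 30.5)/(24.5 × 0.5) = 16.2, penalised-likelihood p=0.009. A Wald interval around this estimate is 0.87-302 and includes 1, so the inference should also come from the penalised likelihood.
- With 3/30 v 0/30: Firth OR = (3.5 × 30.5)/(27.5 × 0.5) = 7.8, p=0.10.

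**3. How often a zero cell arises.** Assumed: a binary marker split 30/30. The group risks r0 and r1 solve (r0 + r1)/2 = event rate with the stated odds ratio. For a 10% rate and OR 10, r0=0.0213 and r1=0.1787. Full group involvement is negligible, so P(zero cell) = (1−r0)^30 + (1−r1)^30 − their product = 0.524 + 0.003 − 0.001 = 0.526.

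Power is the summed probability of all 2×2 tables with p<0.05. Separated tables count as non-significant for Wald.

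| Event rate (expected events) | Zero cell, OR 5 | Zero cell, OR 10 | Power at OR 10: Wald | Fisher | Firth | Likelihood ratio |
|---|---|---|---|---|---|---|
| 5% (3) | 62% | 76% | 0.3% | 4% | 22% | 40% |
| 10% (6) | 32% | 53% | 10.5% | 30% | 54% | 66% |
| 20% (12) | 7% | 21% | 63% | 78% | 86% | 89% |
| 30% (18) | 1% | 5% | 90% | 93% | 96% | 97% |

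- Type I error (OR 1, nominal 5%): Firth 2.7-4.9% over these rates; likelihood ratio about 6-8% (7.5% at the 10% rate).
- Wald power can fall as the effect grows. At the 20% rate it is 63% at OR 10 and 53% at OR 20, while likelihood-ratio power rises from 89% to 97%.
- With 30% marker prevalence and OR 10, the zero-cell probabilities are lower: 57%, 25%, 3% and 0%.

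**4. Continuous markers** (simulated, N=60)
- One marker, OR 3-5 per SD: separation in at most about 4% of data sets at the 5% rate, under 1% at 10% and none at 20%.
- Five covariates, one with OR 3 per SD: 16% at 3 events, 1% at 6 and 0% at 12.
- Eight covariates: 51%, 10% and 0.3%.

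**The case against.** The case against is substantial, and much of it stands.

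- *The Wald test is not specified.* True. A reader might infer that the plan will necessarily declare the strongest predictors non-significant. The documents do not support that: a likelihood-ratio test on the same fit gives p=0.0027 in the example. But no other test is specified either. The likelihood-ratio test is somewhat anti-conservative here, and it leaves the odds ratio and its upper limit infinite.
- *The markers are largely continuous.* The plan describes percentage of positive cells, and the NIH indices are numerical scores. For one such marker, separation is rare. The concern is about categorical predictors, of which the plan lists many (sex, ethnicity, histological class, comorbidities, treatments), and about multivariable models with few events.
- *The event count may be higher.* A reader might take 3-12 from the first quoted range alone. The second range reaches 18, where separation is uncommon. Follow-up varies for biopsies from 2000 onward, and the sample may be expanded.
- *Fisher's test would contradict the regression.* A reader might infer this, but no Fisher test on end-stage disease is clearly planned. Equally, the Fisher provision does not fill the gap, and it gives no adjusted estimate.
- *This is an exploratory proof of concept with a statistician, room for other methods and conspicuous warning signs in the output.* True, and it lowers the weight of the point. But a method chosen after seeing the results is not pre-specified.

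**Conclusion.** The point holds as a conditional risk. The plan applies logistic regression to an outcome that may have only 3-18 events and does not say how sparse data will be handled or which test gives the p-value. For a strong binary predictor the risk is high at 3-6 expected events (zero cell in 53-76% of data sets at OR 10), moderate at 12 (21%) and small at 18 (5%). It is small for a single continuous marker throughout.

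The loss of significance depends on using Wald statistics, which are the usual default but not stated in the plan. The odds ratios, the marker split and the covariate counts are assumptions, because the documents give none. The event rates come from the Introduction's background figures and are not forecasts for this cohort. This is an inexpensive improvement to an exploratory analysis. It is not a flaw that invalidates the study.

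**What to change.** Add one sentence to the Statistical Analysis section: logistic models for end-stage renal disease, and for any other outcome or predictor with sparse cells, univariate or multivariable, will be fitted by Firth penalised likelihood, with p-values and 95% confidence intervals from the penalised profile likelihood instead of Wald statistics.

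The cost is that sentence. Standard software does this, and no new data or patients are needed. Odds ratios are pulled slightly towards 1. The method does not create information: results resting on about 3 events stay uninformative (Firth p=0.10 even when all 3 fall in one group) and should be reported as such.

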## **TIMELINES**

Development of the definitive protocol: month 1.

Submission and Approval by Ethics Committee: months 1-3.

Renal samples identification and preparation: months 4-5.

Informed consent signatures: months 4-6.

Shipment of renal samples: months 4-6.

Anatomo-pathological and laboratory studies: months 7-12.

Review of clinical charts: months 7-12.

Monitoring of the database: months 13-15.

Statistical analysis: month 16.

Elaboration of the final report: month 17-18.

